#### **3.2 Subject Withdrawal from the study**

Subjects are free to withdraw from participation in the study at any time and for any reason, or no reason at all upon request, without prejudice.

An investigator may discontinue or withdraw a subject from the study for the following reasons:

1. Any pathological event, clinical adverse event, laboratory abnormality, intercurrent illness, or any occurrence or change in the subject's physically and/or psychologically status giving indication to the investigator that further participation in the study may not be the best interest of the subject.
2. Subject develops DLT during the study period. (Phase I only)

3. Subject develops disease progression judged by the investigator. (Phase IIa only)
4. The subject's pregnancy from Screening Visit until Final Visit. Subject's pregnancy status should be checked by urine pregnancy test according to the SOA or if investigator or subject suspects the subject is pregnant.
5. The subject was enrolled by error and/or it is discovered that the subject does not meet the eligibility criteria after enrollment.
6. The subject does not take, or is unable to take, the study medication as instructed, does not keep appointments, or otherwise does not adhere to protocol requirements.
7. The subject dies or is lost to follow-up.
8. The study is terminated prematurely by the investigator, research institution, sponsor, IRB/IEC or regulatory authorities.
9. Subject does not receive medical benefit as considered by the investigator

## IX. Concomitant treatment:

### 1. Permitted

#### Life Style Guidance

During this study:

1. Subjects will be advised to abstain from consumption of alcohol during the study.
2. Subjects will be advised to abstain from consumption food containing CYP3A4 inhibitors, as red wine, grapefruit or grapefruit-related citrus fruits (e.g., Seville oranges, pomelos) during the study.
3. Subjects should keep target lesion area(s) or the test skin area(s) clean and dry, avoiding from covering target lesion area(s) or the test skin area(s) with next-to-skin clothes as well as applying reagents other than AR100DP1 topical administration to target lesion area(s) or the test skin area(s).
4. Subjects should avoid from strenuous exercise (e.g., heavy lifting, weight training, calisthenics, aerobics) during the study.
5. Subjects should avoid from water recreation, which is potentially related to water immersion (e.g., swimming, SPA (salus per aqua), hot spring baths, water rafting) during the study.

### 2. Prohibited

The following medications are prohibited until Final Visit:

- **Phase IIa only:** Systemic medication including corticosteroid, immunosuppressant, anti-histamine, phototherapy, or other therapy, which could affect AD within 4 weeks prior to Screening Visit until Final Visit. However, subjects, who have been taking at least 2 weeks of fixed dose anti-histamine prior to Screening and this application does

not affect the study judged by the investigator, are exceptions

- **Phase IIa only:** Topical medication including corticosteroid, immunosuppressant, anti-histamine, phototherapy, calcineurin inhibitors, or other therapy for AD on the target lesion area(s) within 1 week prior to Screening Visit until Final Visit
- Immunosuppressive agents (including azathioprine, mycophenolate, cyclophosphamide, chlorambucil, methotrexate, cyclosporine), or systemic steroid with equivalent dosage higher than prednisolone 30 mg/day for more than 14 days from Screening Visit until Final Visit
- Biologic therapy (including intravenous immunoglobulin) within 12 weeks or 5 half-lives (whichever is longer) prior to Screening until Final Visit
- Any other investigational drug within 4 weeks prior to Screening until Final Visit
- Systemic CYP3A4 inhibitors with strong potency within 1 week prior to Screening Visit, including but not limited to clarithromycin, itraconazole, nefazodone and atazanavir, evaluated by the investigator until Final Visit
- Treatment for any type of cancer (except squamous cell carcinoma, basal cell carcinoma, or carcinoma in situ of the skin, curatively treated with cryosurgery or surgical excision only) within 5 years prior to Screening Visit until Final Visit
- Surgery within 4 weeks prior to Screening Visit until Final Visit

## X. Statistics:

1. **Primary hypothesis:**  superiority  non- inferiority  equivalence  other
2. **Sample size:** Enrolled 35 subjects (Phase I: 21 subjects/Phase IIa: 14 subjects)  
Evaluable 30 subjects (Phase I: 18 subjects/Phase IIa: 12 subjects)
3. **Efficacy population:**  ITT  PP (Phase IIa only)  Other (PP-EOT, Phase IIa only)

**Safety population:**  ITT  PP  Other (MTD, Phase I only)

Intent-to-treat (ITT) population:

- Enrolled subjects receiving at least one dose of AR100DP1

MTD population (Phase I Only):

- Eligible subjects who administered at least one dose of the investigational product and experienced DLT
- OR
- Eligible subjects who were dosed for at least 12 days with at least 85% of compliance.

Per-protocol before End of Treatment (PP-EOT) population (Phase IIa Only):

- A subset of ITT population
- Fulfill all inclusion and exclusion criteria
- Subjects dosed for at least 21 days of Phase IIa with at least 75% of compliance
- No major protocol deviation which could affect the efficacy assessment

- Not take any prohibited therapy before End of Treatment (EOT) Visit assessment

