**VI. Endpoints:**

**1. Primary endpoint(s):**

**Phase I:** Determine the MTD of AR100DP1

*MTD is defined as the highest dose level at which < 2 of 6 subjects experienced a dose limiting toxicity (DLT) during Visit 2-6 (DLT observation period).*

**Phase IIa:** Proportion of subjects with the Investigator's Global Assessment (IGA) score of 0 or 1 on Day 29.

**2. Secondary endpoint(s):****Phase I:**Safety:

- Incidence of adverse events (AE) and serious adverse events (SAE) during Visit 2-6
- Change from baseline in vital signs at Visit 2-6
- Abnormality in physical examination at Visit 2-6
- Transition from baseline in electrocardiogram (ECG) result at Visit 3-6
- Change from baseline in laboratory parameters at Visit 3-6

**Phase IIa:**Efficacy:

- Proportion of subjects achieving the Investigator's Global Assessment (IGA) score of 0 (clear) or 1 (almost clear) on Day 8, Day 15, Day 22, Day 36 and Day 43
- Change from baseline of target lesion area(s) on Day 8, Day 15, Day 22, Day 29, Day 36, and Day 43
- Change from baseline in pruritus NRS of itch level on target lesion area(s) on Day 8, Day 15, Day 22, Day 29, Day 36 and Day 43
- Change from baseline in signs of atopic dermatitis (erythema, edema/papulation, excoriation and lichenification) with grading from 0 (none) to 3 (severe) on target lesion area(s) on Day 8, Day 15, Day 22, Day 29, Day 36 and Day 43
- Change from baseline in the total score of the Patient-Oriented Eczema Measure (POEM) on Day 8, Day 15, Day 22, Day 29, Day 36 and Day 43

Safety:

- Incidence of AE and SAE during Visit 2-8
- Change from baseline in vital signs at Visit 2-8
- Abnormality in physical examination at Visit 2-8
- Transition from baseline in ECG result at Visit 3-8
- Change from baseline in laboratory parameters at Visit 3-8

Exploratory:

- Fold change of IgE on Day 15 and Day 29 compared to baseline on Day 1 ( $IgE_{D15}/IgE_{D1}$ ,  $IgE_{D29}/IgE_{D1}$ )
- Fold change of IL-4 on Day 15 and Day 29 compared to baseline on Day 1 ( $IL-4_{D15}/IL-4_{D1}$ ,  $IL-4_{D29}/IL-4_{D1}$ )

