**Per-protocol (PP) population (Phase IIa Only):**

- A subset of PP-EOT population
- Not take any prohibited therapy during the study

Efficacy analysis will be conducted in ITT, PP-EOT and PP population for Phase IIa study.

Demographic, baseline characteristics and safety analyses will be conducted in ITT population for both Phase I and Phase IIa studies. Efficacy results for Phase IIa study will be concluded in ITT population.

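### The 21-day dosing rule drops early withdrawals for progression or no benefit from PP-EOT and PP, so the per-protocol Day 29 response rates can be biased upward by this route; ITT is unaffected

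*Combined protocol and SAP*

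**What the plan says.** Section X (Statistics), item 3, defines three Phase IIa analysis sets. ITT is every enrolled subject with at least one dose. PP-EOT is a subset of ITT with several conditions, one of which is "Subjects dosed for at least 21 days of Phase IIa with at least 75% of compliance". PP is "A subset of PP-EOT population" with a further condition on prohibited therapy. The plan then states: "Efficacy analysis will be conducted in ITT, PP-EOT and PP population for Phase IIa study". In the same place it says that the Phase IIa efficacy conclusion is drawn from ITT.

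The primary endpoint in section VI is "Proportion of subjects with the Investigator's Global Assessment (IGA) score of 0 or 1 on Day 29". Section VII admits only subjects with an IGA of 2 or 3 at screening.

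Section VIII.3.2 begins "An investigator may discontinue or withdraw a subject from the study for the following reasons". For Phase IIa its list includes "Subject develops disease progression judged by the investigator" and "Subject does not receive medical benefit as considered by the investigator". The early termination visit includes an IGA assessment. The analysis of the primary endpoint carries the last observation forward when all later visits are missing.

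**The concern.** A minimum-exposure rule is normally read as a test of whether the subject took enough drug for the result to be informative. Here it can also act as a test of whether the drug worked. A subject who applied every dose for two weeks, worsened, and was withdrawn for progression has too few days of dosing for PP-EOT and so for PP. That subject is not scored as a failure in those sets; the subject is absent from them. The outcome under study then helps to decide who is in the denominator.

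The trial is open-label and single-arm. The judgement that a subject is progressing or not benefiting is the investigator's, and the IGA is an investigator assessment too. With about 14 subjects, one or two exclusions visibly move a percentage. Three response rates will be reported for the same endpoint. If the per-protocol rates are higher only because failures were dropped, they could be misread as a stronger effect in adherent subjects.

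**Working it through.** **Inputs from the documents**
- Phase IIa: 14 enrolled, 12 evaluable (section X, item 2). The totals close: 21 + 14 = 35 enrolled and 18 + 12 = 30 evaluable. The implied loss is 2/14 = 14.3%. No response rate, power or dropout rate is given, so the 12 cannot be derived from the text.
- Treatment lasts 28 days. The PP-EOT minimum is 21 days, and 21/28 = 75%.
- Treatment-period visits after baseline fall on Days 8, 15, 22 and 29.

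**Who is caught.** A subject withdrawn for progression or no benefit at the Day 8 visit, the Day 15 visit, or an unscheduled visit before 21 days of dosing cannot meet the rule. A subject withdrawn at nominal Day 22 can already have dosed on Days 1 to 21 and can stay in PP-EOT.

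**Whether anything else restores them.** LOCF fills a missing score but does not return a subject to a set that excludes that subject. The early termination IGA is collected, but goes unused in PP-EOT and PP for these subjects.

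**How the plan treats the parallel case.** The Phase I MTD population also has an exposure rule (at least 12 days, at least 85% compliance). It is joined by OR to a clause that keeps any eligible dosed subject who had a DLT. The early stopper whose outcome matters is therefore kept in Phase I. PP-EOT has no matching clause.

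**Size.** Let r be the number of responders and k the number of early failures removed by the rule, with no other exclusions. Both are assumptions.
- Rate with everyone kept: r/14
- Rate in PP-EOT: r/(14 − k)
- Ratio: 14/(14 − k), which is 1.08, 1.17, 1.27 and 1.40 for k = 1 to 4

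| k | r = 4 | r = 6 | r = 8 |
|---|---|---|---|
| 0 | 28.6% | 42.9% | 57.1% |
| 1 | 30.8% (+2.2) | 46.2% (+3.3) | 61.5% (+4.4) |
| 2 | 33.3% (+4.8) | 50.0% (+7.1) | 66.7% (+9.5) |
| 3 | 36.4% (+7.8) | 54.5% (+11.7) | 72.7% (+15.6) |
| 4 | 40.0% (+11.4) | 60.0% (+17.1) | 80.0% (+22.9) |

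Differences are in percentage points, from unrounded rates.

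**Other early stoppers.** If m of the k removed subjects would have counted as responders, the PP-EOT rate is (r − m)/(14 − k). This exceeds r/14 only when m/k is below r/14. With k = 2 and m = 1:
- r = 4: 3/12 = 25.0% against 28.6%
- r = 6: 5/12 = 41.7% against 42.9%
- r = 8: 7/12 = 58.3% against 57.1%

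So the net shift can be downward or close to nil.

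**Scale.** Exact 95% confidence intervals are 8% to 58% for 4/14 and 10% to 65% for 4/12.

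**The case against.** The main counter-argument is that the plan concludes on ITT. That set keeps every dosed subject, and an early failure will normally stay in it as a non-responder: all subjects enter with IGA 2 or 3, IGA is taken at early termination, and LOCF carries that score to Day 29. This stands. A reader might infer that the trial's efficacy conclusion is inflated; the documents do not support that.

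A reader might also infer that PP-EOT and PP can lose only failures, so that their rates must be too high. That does not hold either. Withdrawal for these reasons is permitted, not required. The 21-day rule also removes subjects who stop for an adverse event, non-adherence or personal choice, some of whom might have counted as responders. Only the progression and no-benefit route has a fixed direction.

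It is tempting, too, to read the gap between 14 enrolled and 12 evaluable as two expected PP-EOT exclusions. The documents do not define evaluable for Phase IIa, so k = 2 is only an illustration.

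There are fair objections to the remedy:
- Set membership would depend on the investigator's stated reason for withdrawal.
- Failures would be readmitted while other early stoppers stay out, so some asymmetry remains in the other direction.
- Scoring these subjects one way in the per-protocol sets and another way in ITT would be inconsistent. Using one rule in all sets removes this last problem but not the first two.

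Finally, no success threshold is stated and the intervals are wide, so a shift of a few points changes no decision written in the plan. That limits the importance of the point without removing the mechanism.

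**Conclusion.** The point holds in a limited form. A compliant Phase IIa subject withdrawn for progression or no benefit with fewer than 21 days of dosing is excluded from PP-EOT and PP instead of counting as a failure, and nothing else in the text corrects this. By that route the two per-protocol Day 29 rates can be biased upward. With two such subjects among 14, the shift is 4.8 points at 4 responders and 7.1 points at 6; with one it is 2.2 and 3.3 points; with none it is zero.

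These figures assume the responder count, the number of early failures, that all 14 are dosed, and that there are no other exclusions. The net shift across all early stoppers is not fixed by the text. Severity is minor: the affected analyses are additional to the one on which the plan concludes, but they are planned analyses of the primary endpoint and the correction is cheap.

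**What to change.** Add an OR clause to the exposure condition of PP-EOT, modelled on the DLT clause of the Phase I MTD population. It would keep a subject who meets the other PP-EOT criteria, was at least 75% compliant up to the stop, and was withdrawn for disease progression or lack of medical benefit before 21 days of dosing. PP then inherits the clause, subject to its own condition on prohibited therapy. Leave the 21-day rule as it is for subjects who stop for other reasons.

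State that these subjects count as Day 29 non-responders in ITT, PP-EOT and PP alike, so that no subject is scored differently between sets. State also that the withdrawal reason is recorded: section VIII.3.2 lists permitted reasons but does not say this. Label PP-EOT and PP as supportive to ITT, and tabulate exclusions from each by reason. That table will also show any subjects lost through the prohibited-therapy condition, which can act in the same direction.

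The cost is a few sentences before data are seen, with no extra subjects or visits. The per-protocol rates may be slightly lower, and membership of the sets will rest partly on the investigator's stated reason for withdrawal.

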**Per-protocol (PP) population (Phase IIa Only):**

- A subset of PP-EOT population
- Not take any prohibited therapy during the study

Efficacy analysis will be conducted in ITT, PP-EOT and PP population for Phase IIa study.

Demographic, baseline characteristics and safety analyses will be conducted in ITT population for both Phase I and Phase IIa studies. Efficacy results for Phase IIa study will be concluded in ITT population.

**4. Statistical method(s) for efficacy/safety evaluations:**

**General Approach**

Descriptive statistics will be provided for all endpoints by dose level (dose level of Phase I, and RP2D of Phase IIa).

Continuous variables will be summarized by reporting the number of observations, mean, standard deviation, median, interquartile range (IQR = third quartile (Q3) - first quartile(Q1)), Q1, Q3, minimum and maximum.

Categorical variables will be summarized by using frequency tables showing the number and percentage of subjects within a particular category.

**Analysis of the Primary Efficacy Endpoint(s)**

The primary endpoint of the Phase I study is to determine MTD of AR100DP1 in healthy subjects, which is a safety endpoint. Such endpoint will be observed on evaluable subjects. While in the Phase IIa study, the primary endpoint is the proportion of subjects with the IGA score of 0 or 1 (responder) on Day 29. Frequency tables of response rate and change from baseline of IGA score will be presented respectively. The last-observation-carried-forward (LOCF) method will be applied if all subsequent visits are missing.

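### The Phase IIa ITT responder definition has no rule for prohibited AD therapy, so a Day 29 response after such therapy counts as an AR100DP1 response

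*Combined protocol and SAP*

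**What the plan says.** - **Endpoint.** Section X.4 says that in Phase IIa "the primary endpoint is the proportion of subjects with the IGA score of 0 or 1 (responder) on Day 29". Section VI gives the same definition, and uses IGA 0 or 1 again at the secondary time points, including Days 36 and 43. Neither section mentions other therapy.
- **Populations.** Section X.3 defines ITT as "Enrolled subjects receiving at least one dose of AR100DP1". It adds: "Efficacy analysis will be conducted in ITT, PP-EOT and PP population for Phase IIa study". The conclusion is assigned to one of the three: "Efficacy results for Phase IIa study will be concluded in ITT population".
- **Prohibited therapy.** Section IX.2 opens with "The following medications are prohibited until Final Visit". For Phase IIa the list includes systemic treatment that could affect AD and topical AD treatment on the target lesions, with an exception for an established fixed anti-histamine dose.
- **Effect of a breach on the analysis.** It appears only as a membership condition: for PP-EOT, "Not take any prohibited therapy before End of Treatment (EOT) Visit assessment"; for PP, "Not take any prohibited therapy during the study".
- **Missing data.** LOCF in section X.4 applies when no later visit is available. It does not address values observed after prohibited therapy.
- **Withdrawal.** Section VIII.3.2 is permissive: "An investigator may discontinue or withdraw a subject from the study for the following reasons". Progression, non-adherence and lack of benefit are listed; prohibited therapy is not named.

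**The concern.** The Phase IIa objective is the efficacy of AR100DP1, and the phase has a single arm. No comparator shows how much of a response comes from another treatment. If a subject uses, for example, a topical corticosteroid on the target lesion in week 3 and is IGA 1 on Day 29, nothing in the plan prevents that response from being credited to AR100DP1 in the analysis used for the conclusion.

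The gap also leaves a decision open. In an open-label study of about 14 subjects, how one or two such subjects are classified can visibly change the reported rate, so the rule should be fixed before the data are seen.

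**Working it through.** **1. Apply the definitions to one subject.** Take a Phase IIa subject who receives AR100DP1, uses prohibited AD therapy before Day 29, is not withdrawn, and is IGA 0 or 1 on Day 29.

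- ITT (X.3): included, since only enrolment and a dose are needed.
- Responder (VI, X.4): yes, since only the Day 29 IGA counts.
- PP-EOT and PP (X.3): excluded from both, numerator and denominator.
- LOCF (X.4): not triggered, since Day 29 is observed.
- Withdrawal (VIII.3.2): at the investigator's discretion, so staying on study is consistent with the plan.

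**2. Check the carry-forward route.** Under section VIII.3.1, if withdrawal is decided at a scheduled visit before end of treatment, or at an unscheduled visit, that visit becomes the Early Termination (ET) visit. For a subject withdrawn at a flare, the IGA carried forward is then the one taken at the flare, probably a non-response. The route stays open if the therapy was started before that visit, or if the decision falls between visits and the ET visit follows, within 7 days after the last dose. An ET IGA taken after prohibited therapy could then be carried to Day 29.

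**3. Size.** The plan states no expected response rate, null rate, power or frequency of prohibited therapy, so there is no planned response figure to reproduce. Its sample sizes (X.2) add up: 21 + 14 = 35 enrolled and 18 + 12 = 30 evaluable, with 14 and 12 for Phase IIa.

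Let n = ITT subjects, r = responders without prohibited therapy, m = users of prohibited therapy with IGA 0 or 1, and k = all users (k ≥ m).

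- ITT as written: (r + m)/n
- ITT with users as non-responders: r/n
- Difference: m/n, which is never negative
- PP-EOT, if prohibited therapy is the only reason for exclusion: r/(n − k)

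With n = 14, m/n is 1/14 = 7.1 points, 2/14 = 14.3 points and 3/14 = 21.4 points. If only 12 subjects were in ITT, one subject would be 1/12 = 8.3 points.

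Illustration with 6 observed responders among 14, so 6/14 = 42.9% as written (exact 95% CI 17.7 to 71.1). The 6, the values of m, and k = m are assumptions.

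| m | Users as non-responders (exact 95% CI) | Users dropped, as in PP-EOT |
|---|---|---|
| 1 | 5/14 = 35.7% (12.8 to 64.9) | 5/13 = 38.5% |
| 2 | 4/14 = 28.6% (8.4 to 58.1) | 4/12 = 33.3% |
| 3 | 3/14 = 21.4% (4.7 to 50.8) | 3/11 = 27.3% |

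**4. Why dropping users is a different analysis.** The gap between the last two columns is r/(n − k) − r/n = rk/[n(n − k)]. For r = 4 and k = 2 this is 8/168 = 4.8 points. If those two users had not reached IGA 0 or 1 (m = 0), ITT as written would be 4/14 = 28.6% and PP-EOT 4/12 = 33.3%: the restricted population then shows the higher rate because two failures were removed.

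**The case against.** The strongest reply is that ITT analysis often counts outcomes as observed whatever else the subject took, so the plan may simply be following that approach. It is a recognised choice, and preferring non-responder scoring is partly judgement. But the plan does not state the choice, and without a control arm the as-observed rate mixes the product's effect with that of other therapy.

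The route is also narrow. Section IX.1 tells subjects to put nothing but AR100DP1 on the treated area, section IX.2 bans the therapies, and section VIII.3.1 limits carry-forward as described. What remains is a subject who breaches these rules and is either kept on study or assessed at ET afterwards.

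Stronger readings that a reader might infer, and that the documents do not support:

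- *That the response rate is always inflated.* A user who does not reach IGA 0 or 1 adds nothing to the numerator, and a user who would have responded anyway is not a false response.
- *That PP-EOT and PP are necessarily biased upward.* This depends on whom they exclude. Other exclusions could remove true responders and lower the rate.
- *That the non-responder figure cannot be obtained.* PP-EOT responders divided by the ITT n gives it when prohibited therapy is the only exclusion affecting responders, and a conservative bound otherwise. It is not a planned or concluding analysis, but a reader could form it from the planned tables.
- *That a success decision would be reversed.* The primary endpoint has a frequency table, with no threshold or test, and the intervals in the table overlap heavily.

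**Conclusion.** The concern holds as a gap in the ITT responder rule. The plan is silent rather than explicit, but applied literally it counts a Day 29 IGA of 0 or 1 reached after prohibited AD therapy as an AR100DP1 response in the population used for the conclusion. Against non-responder scoring, the effect is zero or upward: 7.1 points for each such subject with IGA 0 or 1. That figure assumes all 14 planned subjects are dosed. The number of such subjects is unknown, so the total effect cannot be predicted and may be nil. PP-EOT and PP do not supply the missing rule, because they remove users instead of scoring them and are not the basis of the conclusion. This is an inexpensive improvement, not a flaw that invalidates the phase.

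**What to change.** In sections VI and X.4, define an ITT responder as IGA 0 or 1 with no use, before the assessment, of the systemic AD therapy or target-lesion topical AD therapy that section IX.2 prohibits. Name these two categories, because section IX.2 also lists items unrelated to AD. Keep the fixed-dose anti-histamine exception, and the prescribed topical use on non-selected areas that section III.4 allows when lesions exceed 750 cm².

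State that subjects with such use stay in the ITT denominator as non-responders from the date of use, including at Days 36 and 43, and that IGA values recorded after such use are not carried forward as responses. Report the as-observed ITT rate as a sensitivity analysis.

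The cost is a few sentences. No new data are needed, since concomitant medication is recorded at every visit, and nothing changes in how subjects are managed. The reported rate may be slightly lower, and a user who would have responded anyway is scored as a failure. The rule does not isolate AR100DP1 completely: treatment of non-selected areas remains allowed, and section VI does not say that the IGA is confined to the target lesions.

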### Phase IIa:

- (1) Dated and signed informed consent
- (2) Either gender,  $\geq 20$  years old (the legal age of consent majority is 20 years old in Taiwan)
- (3) Confirmed clinical diagnosis of atopic dermatitis (based on the criteria of Hanifin and Rajka for AD)
- (4) With at least 0.5% body surface area (BSA) as target lesion area(s)
- (5) Clinical diagnosis of AD that has been clinically stable, which means the IGA score stays as 2 or 3 when evaluated for  $\geq 4$  weeks at the investigator's discretion prior to Screening Visit
- (6) With Investigator's Global Assessment (IGA) score of 2 (mild) or 3 (moderate) at screening
- (7) Subject of childbearing potential must agree to use abstinence to intercourse, or highly effective contraceptives from signing informed consent to 14 days after the last dose of study drug administration.

At least two forms of effective birth control must be adopted for contraception, and one of which must be a barrier method. Acceptable forms include:

- Established use of oral, injected or implanted hormonal methods of contraception
- Placement of an intrauterine device (IUD) or intrauterine system (IUS)
- Barrier methods of contraception: condom (highly recommended with spermicide),

or occlusive cap (diaphragm or cervical/vault caps)

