- Obtain blood samples for laboratory tests
- Evaluate IGA score
- Self-evaluation of pruritus NRS on target lesion area(s)
- Evaluate signs of atopic dermatitis on target lesion area(s)
- Self-evaluation of POEM score
- Obtain blood sample for tests of immune response (IgE, IL-4)
- Measuring and recording of target lesion area(s)
- Dispense diary and IP
- Retrieve diary and IP
- Record concomitant medications
- Record adverse events
- Other activities per Investigator's decision

➤ **Early Termination Visit (ET)**

*ET, early termination, is defined as the decision of withdrawal is made prior to Visit 6. Subjects will be requested to complete the coming scheduled visit as ET Visit within 7 days after the last dose.*

- Perform urine pregnancy test
- Obtain vital signs
- Obtain weight
- Perform physical examinations

- Perform ECG
- Obtain blood samples for laboratory tests
- Evaluate IGA score
- Self-evaluation of pruritus NRS on target lesion area(s)
- Evaluate signs of atopic dermatitis on target lesion area(s)
- Self-evaluation of POEM score
- Obtain blood sample for tests of immune response (IgE, IL-4)
- Measuring and recording of target lesion area(s)
- Retrieve diary and IP
- Record concomitant medications
- Record adverse events
- Other activities per Investigator's decision

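### Phase IIa Day 29 IGA rate: LOCF can count an early stopper as a responder with no Day 29 response observed; non-responder imputation would be a better primary ITT rule

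*Combined protocol and SAP*

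**What the plan says.** Section X.4 (Analysis of the Primary Efficacy Endpoint(s)) defines a Phase IIa responder as IGA 0 or 1 on Day 29. Its one sentence on missing data is: "The last-observation-carried-forward (LOCF) method will be applied if all subsequent visits are missing".

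Section X.3 sets the population: "Efficacy results for Phase IIa study will be concluded in ITT population". ITT means "Enrolled subjects receiving at least one dose of AR100DP1", so a subject who stops early stays in the analysis. PP-EOT and PP are also analysed. PP-EOT requires, among other things, "Subjects dosed for at least 21 days of Phase IIa with at least 75% of compliance" and "Not take any prohibited therapy before End of Treatment (EOT) Visit assessment".

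In the Phase IIa part of Section VIII.2, withdrawal decided before Visit 6 (Day 29) leads to an ET visit that includes an IGA: "Subjects will be requested to complete the coming scheduled visit as ET Visit within 7 days after the last dose". Under Section VIII.3.1, if withdrawal is decided at a scheduled visit before end of treatment, that visit itself becomes the ET visit. IGA is also scheduled on Days 36 and 43, after treatment has ended.

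The supplied text gives no non-responder rule and no sensitivity analysis for missing data.

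**The concern.** The endpoint is a response on a stated day. Under LOCF, a score of 0 or 1 from an earlier day stands in for Day 29 when the subject has left the trial. Several withdrawal reasons in Section VIII.3.2 say nothing about poor response: an adverse event, pregnancy, an eligibility error, non-adherence, loss to follow-up or the subject's own choice. Someone who leaves for one of these reasons with a good last score is reported as a Day 29 success, although no end-of-treatment response was seen.

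The trial is uncontrolled, so no comparator arm would be affected in the same way. The ITT rate is the main efficacy result of Phase IIa, and with 14 subjects each classification shows in it.

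A narrower point concerns a subject who misses Day 29 but attends Day 36 or Day 43. The LOCF condition then fails, and the text does not say whether that subject stays in the denominator.

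**Working it through.** **Inputs from the plan**
- Planned Phase IIa numbers: 14 enrolled, 12 evaluable (Section X.2).
- Visit 6: Day 29 ± 2 days, so Day 27 to Day 31 (Section XI, Phase IIa schedule).
- ET visit: within 7 days after the last dose (Section VIII.2).
- Not given: a dropout rate, a target response rate, or an expected number of early stoppers. Response counts below are assumptions.

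**1. The plan's own figures.** 14 − 12 = 2 subjects, or 2/14 = 14.3%. At that fraction 12/(1 − 1/7) = 14, and for Phase I 18/(1 − 1/7) = 21, which match the stated enrolment. With no stated dropout rate this is only a consistency check. It shows an apparent allowance of two non-evaluable Phase IIa subjects.

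**2. Can a score from outside the window be carried forward?**
- Last dose on Day 19: latest on-time ET visit is Day 19 + 7 = Day 26, before the window opens.
- Last dose on Day 20: Day 20 + 7 = Day 27, the first case in which an on-time ET visit can fall inside the window.

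So with the last dose on Day 19 or earlier, an on-time ET score always precedes the Day 29 window. Section VIII.3.1 asks for a Final Visit only when withdrawal is decided after end of treatment. An early stopper therefore normally has no later visit, and the LOCF condition is met.

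**3. Size, with all 14 subjects dosed.** Each carried response adds 1/14 = 7.1 points, and two add 2/14 = 14.3 points, whatever the observed count. As an illustration, assume 2 early stoppers and 4 responses observed on Day 29 among the other 12:

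| Early stoppers carried as responders | ITT rate | Exact 95% CI |
|---|---|---|
| 0 (both non-responders) | 4/14 = 28.6% | 8.4% to 58.1% |
| 1 | 5/14 = 35.7% | 12.8% to 64.9% |
| 2 | 6/14 = 42.9% | 17.7% to 71.1% |

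The intervals are Clopper-Pearson. A shift of 7.1 points is small beside their width.

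**4. Missed Day 29, later visit attended.** LOCF does not apply, and the natural reading is that nothing is imputed. With one such subject and r responders among the other 13, the rate is r/14 if the subject is kept as a non-responder and r/13 if excluded. The difference is r/182.

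| r (assumed) | Kept, r/14 | Excluded, r/13 | Difference |
|---|---|---|---|
| 3 | 21.4% | 23.1% | 1.6 points |
| 5 | 35.7% | 38.5% | 2.7 points |
| 7 | 50.0% | 53.8% | 3.8 points |

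**The case against.** The case for leaving the text alone is fair, and much of it stands.

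- **LOCF is prespecified.** Carrying the last score of someone who stops is what the method does. The plan neither contradicts itself nor omits a rule for that subject. This stands, so the point is an improvement in method and not an error.
- **Nothing turns on the rate.** The plan says "Descriptive statistics will be provided for all endpoints by dose level", and the supplied text sets no success threshold for this endpoint. A reader might infer an inflated false-positive risk or an invalid conclusion. The documents do not support that, because no test of this rate is described.
- **Many carried scores will be non-responses.** Entry requires an IGA "score of 2 (mild) or 3 (moderate) at screening", so a carried response would ordinarily have appeared after dosing began. Subjects withdrawn for progression or lack of benefit would probably carry a non-response. This stands, and it is why the effect is only possible.
- **PP-EOT and PP give supportive rates.** This stands in part. The conclusion is drawn in ITT, and those sets give no rule for a missing Day 29. A subject whose last dose is on Day 21 and whose ET visit is on Day 22 could meet the 21-day criterion and still be carried forward.
- **The gap at a missed Day 29 is narrow.** One might add a third option, counting the subject as a responder, and so a span of about 7 points. That would need an imputation the plan does not provide. Only the denominator is open, and the ITT definition points towards keeping the subject.
- **Visit mapping.** A subject who stops after Visit 5 has Visit 6 as the coming visit, so the ET score might be entered as end of treatment even before Day 27. The text does not settle this, and the new wording should.

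**Conclusion.** The point holds as a minor, cheap improvement. The stated rule lets an ITT subject count as a Day 29 responder without a Day 29 observation. Relative to non-response this can only raise the rate, by 7.1 points per subject, or 14.3 points if both subjects in the plan's apparent allowance stopped early with IGA 0 or 1. That count is an assumption, as is the dosing of all 14 subjects. The documents do not support a larger number.

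It would be too strong to say that the reported rate will be biased upward. True Day 29 status is unknown for these subjects: a carried response may be correct, and a carried non-response may understate the result. The claim concerns crediting responses that were not observed.

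The missed Day 29 with later attendance is secondary, at about 2 to 4 points for one subject over the counts assumed. The supplied text is headed as a synopsis, so the statement that no other rule exists is limited to it.

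**What to change.** Replace the LOCF sentence in Section X.4 with wording such as:

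> In the primary ITT analysis of Day 29 IGA 0/1, all treated subjects stay in the denominator. The observed Visit 6 (EOT) IGA is used, including one taken slightly outside the ± 2 day window by a subject who completed treatment, with the visit-window deviation reported. An ET IGA is used only if it falls within the Day 29 window. A subject with no such assessment is a non-responder, whether or not Day 36 or Day 43 is attended. LOCF and observed-case results are reported as sensitivity analyses.

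The sponsor should fix in days, before the data are reviewed, what slightly outside means. The Visit 7 window opens on Day 33 (Day 36 − 3), so the margin should end before then. Accepting a slightly late Visit 6 score matters: a strict Day 27 to 31 cut-off would turn a completer's observed response, taken a day late, into a non-response.

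The cost is analysis wording only, with no new visits or data. The stated rate may be lower by 7.1 points per affected subject, and the rule is conservative for true responders who were not assessed. The LOCF sensitivity analysis will show how much this matters.
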